## **1. Research background**

According to the 2022 guidelines for perioperative care for liver surgery, implementing Enhanced Recovery After Surgery (ERAS) in liver surgery may improve postoperative outcomes. Compared with open hepatectomy, laparoscopic hepatectomy has the advantages of less postoperative hospitalization time and lower complication rates, which is recommended in well-trained teams and clinically appropriate situations. Postoperative pain after laparoscopic liver resection is composed of multiple factors, including somatic and visceral pain, which is caused by abdominal distension, laparoscopic port position and abdominal wall wounds. The peak pain of postlaparoscopic surgery mainly occurs in the first 24 hours, it is particularly significant to find an appropriate way to relieve pain.

Epidural analgesia has been the gold standard for perioperative pain control, but it is associated with longer hospitalization time and increased hospital costs and a higher incidence of urinary tract infections. Additionally, its use is limited by an increasing number of drugs that interfere with blood coagulation function. Regional anesthesia is an important component of multimodal analgesia, which can reduce the dosage of opioids after surgery, thereby reducing the occurrence of adverse reactions and it is helpful for postoperative recovery. Transversus abdominis plane block (TAPB) and Rectus sheath blocks (RSB) are widely used in abdominal surgery. TAPB blocks the sensory nerves of the anterolateral abdominal wall (T6-L1), and a Meta-analysis has shown that it is effective as epidural analgesia while having fewer episodes of hypotension. Bilateral rectus sheath blocks (RSB) was originally introduced to loosen the abdominal wall during surgery by blocking the terminal branches of the 9th, 10th and 11th intercostal nerves between the internal oblique and transversus abdominis muscles. It has now been shown to reduce opioid use and alleviate postoperative pain, but if the needle tip is too deep during RSB, it will have the risk of puncturing the abdominal organs. The limitation of both TAPB and RSB lies in their ability to provide somatic analgesia only without visceral analgesia.

Some studies have applied Erector spinae plane block (ESPB) in abdominal surgery where it can act on both the ventral and dorsal branches of spinal nerves, further enhancing visceral analgesia by blocking sympathetic nerve. Altıparmak et al compared ultrasound-guided ESPB with oblique subcostal TAPB for postoperative pain relief in patients undergoing laparoscopic cholecystectomy, and proved that ESPB could reduce tramadol consumption and pain score more effectively. Kamel et

al. [9] concluded that bilateral ESPB provides longer duration of postoperative analgesia and less morphine consumption than TAPB in patients undergoing open abdominal total hysterectomy. In open hepatectomy, ESPB has been proved to have better analgesic properties than oblique subcostal TAPB, specifically manifests in lower postoperative pain scores, longer time to first need for morphine, and less morphine consumption. The analgesic effect of ESPB has been demonstrated after abdominal surgery.

The analgesic and postoperative recovery effects of ESPB have not been compared with TAPB combined with RSB in patients undergoing laparoscopic hepatectomy.

## **2. Study Purpose**

Comparing the postoperative analgesic and recovery effect of TAPB combined with RSB and ESPB in patients undergoing laparoscopic hepatectomy.

## **3. Study design**

### **3.1 Study types**

single-center, prospective, randomized, double-blind, controlled study

### **3.2 Random grouping**

Patients were randomly divided into two groups according to computer generate random number table: TAPB combined with RSB group (control group) and ESPB group (experimental group). Group assignment information was stored in a sealed opaque envelope and stored and distributed by a specific person.

### **3.3 Double-blind**

All patients included in the study were required to sign informed consent. Before anesthesia induction, the experimental group received ESPB while the control group was given TAPB combined with RSB. The abdominal incision and puncture points due to the block were covered with sterile dressings in both experimental and control groups after surgery. The anesthesiologist who performed the nerve block carries out the corresponding nerve block according to the groups in the envelope. Anesthesiologists responsible for anesthesia management, surgeons, and those conducting postoperative follow-up visits were unaware of the group situations.

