### **5. Sample estimation**

The sample size was calculated based on previous literature, requiring 27 patients per group to achieve a two-sided 0.05 significance level and 90% power of the test. A sample size of 60 was required to set a dropout rate of 10%.

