### **6. Research process**

The experiment was carried out in Tongji Hospital, Tongji Medical College, Huazhong University of Science and Technology. For patient who were going to undergo laparoscopic partial hepatectomy, anesthesiologists went to the ward one day before surgery for preoperative evaluation, signed the informed consent form, and screened the subjects according to the inclusion and exclusion criteria. In according with the random results, the patients were randomly divided into ESPB group (experimental group) and TAPB&RSB group (control group). The patients were instructed to use analgesic pump and visual analogue scale (VAS). (Visual analogue scale (VAS): a 100 mm transverse line with 0mm at one end of the line indicates no pain, 100mm at the other end indicates severe pain and the middle part shows different levels of pain.)

1) All patients were routinely fasted before surgery, and no preoperative medication was given.

2) After entering the operation room, the patients in the experimental group and the control group took the sitting position, and the VAS scores of the patients in the resting state and the cough state were recorded. The subjects were scored preoperatively using the QoR-15 patient questionnaire (see supplementary).

3) Electrocardiogram, blood pressure, pulse, and blood oxygen saturation were monitored. After local anesthesia, ultrasound-guided internal jugular vein catheterization was performed, which could monitor central venous pressure (CVP) and record preoperative CVP after connecting the transducer.

4) The experimental group received ultrasound-guided ESPB, and bilateral ESPB was performed at T7 segment with 20ml 0.375% ropivacaine on each side. While the control group receives ultrasound-guided TAPB combined with RSB, which was performed under the costal margin with 10ml 0.375% ropivacaine for bilateral TAPB and 10ml 0.375% ropivacaine for bilateral RSB.

5) Anesthesia was induced with methylprednisolone 5mg, dexamethasone 5mg, penehyclidine hydrochloride 0.5 mg and palonosetron 0.25 mg, sufentanil  $0.5\mu\text{g}\cdot\text{kg}^{-1}$ , etomidate  $0.15\text{-}0.20\text{ mg}\cdot\text{kg}^{-1}$  and cisatracurium  $0.20\text{mg}\cdot\text{kg}^{-1}$ .

6) Tracheal intubation was performed after 5 minutes of mask oxygen inhalation; Ultrasound guided radial artery puncture catheterization was performed to monitor ambulatory blood pressure.

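### The double-blind label is not secured: patients receive the block before induction at a body site that differs by arm, and the dressing rule as written could show assessors the arm

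*Combined protocol and SAP*

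**What the plan says.** Section 3.1 describes a "single-center, prospective, randomized, double-blind, controlled study". Section 3.3 then sets out the masking in three statements:

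- Timing: "Before anesthesia induction, the experimental group received ESPB while the control group was given TAPB combined with RSB".
- Concealment: "The abdominal incision and puncture points due to the block were covered with sterile dressings in both experimental and control groups after surgery".
- Roles: "Anesthesiologists responsible for anesthesia management, surgeons, and those conducting postoperative follow-up visits were unaware of the group situations". The anesthesiologist who performs the block opens the envelope and so knows the arm. Patients are not mentioned.

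Section 6 gives the order of events. In step 1, "no preoperative medication was given". In step 2 patients sit and score their pain. In step 3, "After local anesthesia, ultrasound-guided internal jugular vein catheterization was performed". Step 4 is the block: in the experimental arm "bilateral ESPB was performed at T7 segment", and in the control arm TAPB plus RSB below the costal margin. General anesthesia is induced only in step 5. Section 1 places the TAPB on the anterolateral abdominal wall.

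Under section 8.1 the primary outcome is 24-hour morphine consumption. The secondary outcomes include rescue analgesia, VAS at rest and on coughing, and QoR-15. Steps 9 and 10 of section 6 let patients press the pump themselves, and on the ward rescue may be given at the patient's request.

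**The concern.** Double-blind is normally taken to include the patient. Here the patient has had no premedication, and the needles go to a different part of the body in each arm. Nothing described in the plan would stop the patient from noticing where. The same person then decides when to press the pump and supplies the pain and recovery scores.

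The masking of follow-up staff is the remaining protection for these outcomes. It rests on a statement that they are unaware and on a dressing rule. If the position of a dressing differs by arm, the rule meant to hide the arm could disclose it. At stake is whether the main comparison can be reported as double-blind, and whether assessor masking is achieved or only asserted.

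**Working it through.** **The plan's own figure.** The only figure nearby is the total sample size in section 5: 27 / (1 − 0.10) = 30 per group, and 2 × 30 = 60. It reproduces. The masking point does not depend on it, and the fix leaves it unchanged. The rest of the check sets the sections side by side.

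**Patients.**

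1. Sections 3.3 and 6 agree that the block (step 4) comes before induction (step 5).
2. Step 1 rules out premedication. Steps 2 to 4 mention no sedative, and the only anesthetic before the block is local, for the jugular line. No sham injection or screen is described.
3. The control sites are on the abdominal wall. That the ESPB at T7 is given on the back is an inference from the name and level of the block; the protocol does not say so.
4. Section 3.3 names three unaware roles, and the patient is not one of them. No other section says that patients are masked.

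Patients therefore cannot be assumed masked.

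**Follow-up staff.** The dressing sentence allows two readings:

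| Reading | ESPB arm | TAPB plus RSB arm | Does position show the arm? |
|---|---|---|---|
| Literal: incision and actual puncture points | abdomen and back | abdomen only | Yes, if the back is seen |
| Common scheme: same sites in everyone | abdomen and back | abdomen and back | No |

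The reference to both groups fits either reading. No sentence requires a dressing over a site that was not punctured, so staff who follow the text exactly would produce the first row.

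**Surgeons.** Section 3.3 calls them unaware, but the dressings are applied after surgery. The control punctures are in the abdominal wall, where the surgeon works. The dressing rule cannot conceal those marks during the operation, and no other measure is described.

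**Outcomes exposed.**

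- Primary outcome: partly driven by patient presses, because the pump also has a background infusion.
- VAS and QoR-15: reported by the patient.
- Rescue: triggered by the patient's own score or, on the ward, by request.

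The documents give no figure from which a bias could be calculated, and none is claimed.

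**The case against.** The strongest reply is that both arms receive an active block. Knowing where the needle went is not knowing which arm is expected to do better. Nothing in the available text tells patients which is favoured, and the consent pages are not available to check. This stands as a limit on the likely harm and is why no size or direction of bias is given. It does not make patients masked.

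A second reply is that double-blind may be meant for clinicians and assessors. Section 3.3 is compatible with that but does not say so. A reader might go further and infer that the plan leaves all masked roles undefined. That is not supported: section 3.3 names three unaware roles and one unmasked role, and only the patient's status is left open.

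Third, the dressing sentence may intend a common scheme, and no section has assessors inspecting the back. Both points are fair. Disclosure through a dressing is therefore a possibility that the text permits, not something shown to happen.

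A reader might also infer that the managing anesthesiologists, or whoever records CVP after the block, learn the arm. The documents do not support this. Section 3.3 separates the managing anesthesiologists from the person who performs the block and states that they are unaware. Silence about who is in the room is not a contradiction, and nothing shows that the CVP recorder learns the arm.

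**Conclusion.** The point holds in this form: the plan claims double-blinding, does not secure it for patients, and states assessor masking without a rule that reliably delivers it. Surgeon masking during the operation is likewise asserted without a means of concealment. The plan should be changed, but the trial remains interpretable.

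The size and direction of any bias are unknown. A reader might infer that the primary result must be biased, or biased towards ESPB. The documents do not support that, since both blocks are active and patients' expectations are not documented. Counting the patient-reported items would show how widely the exposure reaches, but would not measure bias.

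The conclusion rests on three assumptions: that ESPB at T7 is given on the back; that silence about sedation during the block means none is given; and, for the assessors only, that the dressing rule is followed literally.

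**What to change.** 1. In section 3.3, require that every patient, whichever block was given, has identical opaque dressings over the same back and abdominal block sites, in place before the first assessment at 1 h.
2. Instruct patients not to tell assessors where the needles were placed.
3. Restate sections 3.1 and 3.3 by role. Follow-up assessors: blinded. Patients: not blinded, unless a masking procedure for them is added. Surgeons: blinded only if the abdominal puncture sites are actually concealed from them.
4. Report patient awareness as a limitation for the patient-driven and patient-reported outcomes: pump consumption (including the primary), rescue, VAS and QoR-15.

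The cost is a few extra dressings per patient, wording changes in two sections, and loss of the unqualified double-blind label. Sample size and analysis are untouched. The dressings protect the assessors; patient awareness remains. If enrolment has finished, items 3 and 4 still apply, but assessors should then be described as blinded only as far as the dressings actually used support it.

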## **4. Selection and withdrawal of subjects**

#### **4.1 Inclusion criteria**

- 1)ASA grades I-II
- 2)age 18~70 years old
- 3)BMI 19~28 kg/m^2
- 4)patients undergoing elective laparoscopic partial liver resection

#### **4.2 Exclusive criteria:**

- 1) The nerve block cannot be performed, such as skin infection at the puncture site
- 2) Daily using the opioid analgesics or have a history of opioid abuse
- 3) Allergy or a history of drug allergy to any of the drugs used in the study
- 4) Patients have cognitive impairment, mental or neurological diseases, motor or sensory deficits
- 5) Coagulation disorders
- 6) Severe lung, heart, liver, or kidney dysfunction
- 7) Participating in other clinical trials within 3 months before being included in this study

### **5. Sample estimation**

The sample size was calculated based on previous literature, requiring 27 patients per group to achieve a two-sided 0.05 significance level and 90% power of the test. A sample size of 60 was required to set a dropout rate of 10%.

### **6. Research process**

The experiment was carried out in Tongji Hospital, Tongji Medical College, Huazhong University of Science and Technology. For patient who were going to undergo laparoscopic partial hepatectomy, anesthesiologists went to the ward one day before surgery for preoperative evaluation, signed the informed consent form, and screened the subjects according to the inclusion and exclusion criteria. In according with the random results, the patients were randomly divided into ESPB group (experimental group) and TAPB&RSB group (control group). The patients were instructed to use analgesic pump and visual analogue scale (VAS). (Visual analogue scale (VAS): a 100 mm transverse line with 0mm at one end of the line indicates no pain, 100mm at the other end indicates severe pain and the middle part shows different levels of pain.)

1) All patients were routinely fasted before surgery, and no preoperative medication was given.

2) After entering the operation room, the patients in the experimental group and the control group took the sitting position, and the VAS scores of the patients in the resting state and the cough state were recorded. The subjects were scored preoperatively using the QoR-15 patient questionnaire (see supplementary).

3) Electrocardiogram, blood pressure, pulse, and blood oxygen saturation were monitored. After local anesthesia, ultrasound-guided internal jugular vein catheterization was performed, which could monitor central venous pressure (CVP) and record preoperative CVP after connecting the transducer.

4) The experimental group received ultrasound-guided ESPB, and bilateral ESPB was performed at T7 segment with 20ml 0.375% ropivacaine on each side. While the control group receives ultrasound-guided TAPB combined with RSB, which was performed under the costal margin with 10ml 0.375% ropivacaine for bilateral TAPB and 10ml 0.375% ropivacaine for bilateral RSB.

5) Anesthesia was induced with methylprednisolone 5mg, dexamethasone 5mg, penehyclidine hydrochloride 0.5 mg and palonosetron 0.25 mg, sufentanil  $0.5\mu\text{g}\cdot\text{kg}^{-1}$ , etomidate  $0.15\text{-}0.20\text{ mg}\cdot\text{kg}^{-1}$  and cisatracurium  $0.20\text{mg}\cdot\text{kg}^{-1}$ .

6) Tracheal intubation was performed after 5 minutes of mask oxygen inhalation; Ultrasound guided radial artery puncture catheterization was performed to monitor ambulatory blood pressure.

7) Maintenance of anesthesia should use 1-2% sevoflurane inhalation, dexmedetomidine  $0.5\mu\text{g}\cdot\text{kg}^{-1}\cdot\text{min}^{-1}$  and fentanyl  $0.1\text{-}0.2\mu\text{g}\cdot\text{kg}^{-1}\cdot\text{min}^{-1}$ , and maintain blood pressure at baseline values of plus or minus 20%. In volume controlled ventilation mode, tidal volume was 6ml/kg, airway pressure was maintained within 25cmH2O, and end-tidal CO2 is maintained 35-45 mmHg. CVP values were recorded at 5, 10, 15, and 30min after nerve block. ECG, HR, BP, SpO2, CVP, PetCO2, BIS value, temperature, liquid intake and output are monitored during operation. Arterial blood gas analysis was used to correct acid-base imbalance and electrolyte imbalance.

8) Analgesic coherence: 30 minutes before the end of surgery, sufentanil 5ug was injected intravenously.

9) The patient was sent to PACU for observation for one hour after awake extubation, and then connected to an analgesic pump: sufentanil 15ug, nojan 15mg, palonosetron 0.3mg, 0.9% normal saline added to 150ml. The background infusion

rate was set according to the weight <50 kg at 1ml/h, 1.5ml/h for 50-60 kg and >70 kg at 2ml/h with a single compression dose of 2ml and a lockout time of 10min. According to the needs of patients, the analgesic pump could be pressed by themselves for analgesia. If pain cannot relieve (VAS>4 at rest), the remedial analgesia with a single dose of 2mg oxycodone can be used. At 1 hour after the end of surgery, recording the VAS scores of patients in resting and coughing states and the dose of analgesic pump. Asking patients if they had any adverse reactions, such as nausea, vomiting, pruritus, dizziness, headache, respiratory depression, etc.

10) After returning to the ward, patients could press the analgesic pump by themselves for additional analgesia. Lack of pain relief (VAS> 4 points) or, at the patient's request, rescue analgesia with a single dose of diclofenac sodium suppository. The dosage of analgesic pump, times of rescue analgesia, VAS scores in the resting and coughing and adverse reactions were recorded at 2h, 4h, 8h and 24h after operation. The QoR-15 patient questionnaire was used to evaluate the postoperative recovery at 24 hours after surgery.

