# **8.Data collection and statistical analysis**

## **8.1 Data collection**

Main observation indicator: consumption of morphine within 24 hours after surgery

Secondary observation indicators

- 1) Morphine consumption at 1h, 2h, 4h and 8h after surgery

- 2) Number of rescue analgesia at 1h, 2h, 4h, 8h and 24 hours after surgery
- 3) VAS scores in resting and coughing at 1h, 2h, 4h, 8h and 24h after surgery
- 4) CVP values at 5, 10, 15 and 30min after nerve block
- 5) QoR-15 patient questionnaire scores before and 24h after surgery
- 6) Postoperative liver function (the percentage increase of AST and ALT compare with preoperative), postoperative complications and discharge time

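### Section 6, step 9 connects the pump one hour after extubation but reads its dose 1 hour after the end of surgery; as written, the pump part of the 1 h consumption outcome is zero in both arms

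*Combined protocol and SAP*

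**What the plan says.** Four statements in the combined protocol and SAP bear on this.

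- **Pump start** (section 6, step 9): "The patient was sent to PACU for observation for one hour after awake extubation, and then connected to an analgesic pump".
- **First pump reading** (same step): "At 1 hour after the end of surgery, recording the VAS scores of patients in resting and coughing states and the dose of analgesic pump".
- **Later readings** (section 6, step 10): pump dosage, rescue, VAS and "adverse reactions were recorded at 2h, 4h, 8h and 24h after operation".
- **Outcomes** (section 8.1): the primary is given as "Main observation indicator: consumption of morphine within 24 hours after surgery", and the first secondary as "Morphine consumption at 1h, 2h, 4h and 8h after surgery".

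The pump runs a weight-dependent background infusion of 1 to 2 ml/h, with 2 ml boluses and a 10-minute lockout. Step 9 also allows 2 mg oxycodone as rescue. The plan does not ask for the time of extubation or of pump connection. It does not say which opioids count as morphine consumption or how they are converted.

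**The concern.** Step 9 uses two clocks. The pump starts on a clock that begins at extubation, while consumption is read on a clock that begins at the end of surgery. Taken literally, the first pump reading falls at or before the moment of connection.

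This has two consequences. First, a listed secondary outcome may contain no pump data, so the between-group test in section 8.2 has nothing to compare at 1 h. Second, because the pump infuses continuously, part of every later total accrues with connected time whatever the patient's pain. A patient extubated late has less pump time inside the same window, and the plan collects nothing that would show it.

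**Working it through.** **The plan's own figures.** The plan states no pump time to reproduce. The only figure that can be recomputed is the total sample size: 2 × 27 = 54, and 54 / (1 − 0.10) = 60, which agrees. Nothing below depends on it.

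**Inputs from the documents**
- Pump start: extubation + 1 h (step 9, literal reading).
- Reading times: 1, 2, 4, 8 and 24 h, all taken as hours after the end of surgery.
- Pump content: "sufentanil 15ug, nojan 15mg, palonosetron 0.3mg, 0.9% normal saline added to 150ml", so the sufentanil concentration is 15 / 150 = 0.1 µg/ml.
- Background rate: 1 to 2 ml/h.

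**Input assumed.** The delay *e* from end of surgery to extubation is not given. I use 10 to 40 minutes (0.17 to 0.67 h), and 0 to 1.5 h as a wide range.

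**Formula.** Pump hours at mark *m* = max(0, *m* − (1 + *e*)).

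| Mark | *e* = 10 min | *e* = 40 min | Ratio |
|---|---|---|---|
| 1 h | 0 | 0 | – |
| 2 h | 0.83 | 0.33 | 2.5 |
| 4 h | 2.83 | 2.33 | 1.21 |
| 8 h | 6.83 | 6.33 | 1.08 |
| 24 h | 22.83 | 22.33 | 1.02 |

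**At 1 h.** The result is 0 for any *e* ≥ 0, so it does not depend on the assumed delay. With a constant zero in both arms the t statistic is 0/0 and all ranks are tied. If rescue oxycodone counts, the 1 h total is 2 mg times the number of doses, which largely repeats the separate outcome of number of rescue analgesia at 1 h.

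**At 2 h.** Pump time varies 2.5-fold over the 10 to 40 minute range. Over the wide range it runs from 1.0 h (*e* = 0) to 0 h (*e* of 1 h or more).

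**At 24 h.** The spread is 0.5 h, and 0.5 / 22.83 = 2.2%. In background sufentanil this is 0.5 h × 1 to 2 ml/h × 0.1 µg/ml = 0.05 to 0.10 µg. Over the wide range pump time runs from 23.0 to 21.5 h, and 1.5 / 23.0 = 6.5%. These amounts leave out boluses. With every bolus used the pump delivers at most about 13 to 14 ml/h (six 2 ml boluses plus background), or 1.3 to 1.4 µg/h, so a lost half hour could matter more for a patient who presses often.

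**Other reading: connected on arrival in PACU.** If connection follows extubation at once, pump hours at *m* = *m* − *e*. The 1 h mark then holds 0.83 to 0.33 h and the 24 h mark 23.83 to 23.33 h. The zero disappears, but the 1 h total now depends on the extubation delay in the way the 2 h total did above.

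**The case against.** The strongest reply is that the pump is probably meant to run in PACU. Step 9 describes self-pressing and oxycodone rescue before it reaches the 1 h record, it expects a pump dose at that record, and step 10 treats pressing on the ward as extra. The opening sentence can be read as sending the patient to PACU for an hour and connecting the pump there. This stands as far as it goes: a reader might infer that the 1 h outcome is zero by design, and the documents do not establish that. What they contain is two sentences that cannot both be followed literally, with no means of telling which one governs.

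It is also fair that section 8.1 lists morphine consumption, not pump dose. With the counted opioids undefined, rescue oxycodone could make the 1 h total non-zero even on the literal reading. The zero therefore applies to the pump component only.

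A reader might go further and infer that the primary comparison is biased. The documents do not support that. Steps 5 to 8 are common to both arms, and section 3.3 keeps those managing the anaesthesia unaware of the group. Unequal pump time biases the comparison only if extubation time differs by arm. Nothing in the plan shows such a difference, though nothing is collected that could exclude it.

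Finally, it is tempting to restart the consumption clock at pump connection. That would take consumption off the end-of-surgery clock it shares with VAS, rescue and the 24 h QoR-15, and would leave out opioid given before connection. That objection is sound, and I do not propose the change.

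**Conclusion.** Wrong as written: an unreconciled contradiction that affects a secondary outcome. On the literal text the pump component at 1 h is zero in both arms whatever the extubation delay, so the 1 h comparison is uninformative or reflects rescue opioid alone. The 2 h total depends strongly on time to extubation (0.83 to 0.33 h of pump time for an assumed 10 to 40 minutes); the 4 h and 8 h totals depend on it progressively less. For the 24 h primary the variation in pump time is about 2% under the same assumption and 6.5% over the wide range. That is noise unless extubation time differs by arm.

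The zero at 1 h rests on the literal order of events in step 9 and on extubation not preceding the end of surgery. The later figures also rest on the assumed delay.

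**What to change.** 1. Reconcile the two sentences in step 9, so that the protocol states one time of pump connection relative to extubation and to the end of surgery. When the pump should be connected is for the sponsor to settle.
2. Keep the end of surgery as time zero for all outcomes, and say so in section 8.1.
3. State which opioids count towards consumption and how they are converted, and count rescue opioid given before the pump is connected.
4. Record the times of end of surgery, extubation and pump connection for each patient, and report pump time within each window by arm.
5. If the pump is not running at 1 h, remove pump consumption from the 1 h outcome and keep VAS and rescue there. If it is running, correct the wording of step 9 and keep the outcome.

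The cost is protocol wording, extubation and connection time stamps (and the end-of-surgery time, if it is not already kept), and possibly one secondary time point. The sample size does not change.

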## **8.2 Statistical analysis**

The Shapiro Wilk test was used to determine the normality of data distribution for measurement data. Measurement data with normal distribution were expressed as mean  $\pm$  standard deviation, and measurement data with non-normal distribution were expressed as median (interquartile range, IQR). Measurement data were compared between groups by t test or Mann-Whitney U test according to whether the data were normal distribution, and VAS scores were compared by repeated measures analysis of variance. Count data were expressed as frequency (%), and compared between groups by using chi-square test or Fisher exact test. The value of P less than 0.05 was considered statistical significance.

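### The pump's background rate depends on body weight, so adding weight to the primary comparison is a cheap, optional gain in precision

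*Combined protocol and SAP*

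**What the plan says.** Section 8.1 names the primary endpoint: "Main observation indicator: consumption of morphine within 24 hours after surgery". The drug comes mainly from a pump filled, under section 6, step 9, with "sufentanil 15ug, nojan 15mg, palonosetron 0.3mg, 0.9% normal saline added to 150ml". Step 9 sets its background infusion by weight: "rate was set according to the weight <50 kg at 1ml/h, 1.5ml/h for 50-60 kg and >70 kg at 2ml/h". Patients add 2 ml doses on demand with a 10-minute lockout: "According to the needs of patients, the analgesic pump could be pressed by themselves for analgesia". Rescue opioid in the recovery unit lies outside the pump: "the remedial analgesia with a single dose of 2mg oxycodone can be used".

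Step 10 lists what is collected on the ward: "The dosage of analgesic pump, times of rescue analgesia, VAS scores in the resting and coughing and adverse reactions were recorded". Neither step lists a press count or a patient-demanded dose. Section 8.1 does not say whether the background counts.

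Section 8.2 gives the between-arm analysis: "Measurement data were compared between groups by t test or Mann-Whitney U test according to whether the data were normal distribution". It names no covariate. Section 3.2 describes no stratification by weight. Section 5 states the size: "requiring 27 patients per group to achieve a two-sided 0.05 significance level and 90% power of the test".

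**The concern.** If consumption is total pump output, part of each patient's value is set by weight alone. The lightest and heaviest bands differ by 23 ml over 23 hours, about eleven demand presses, for a reason unrelated to either block. An unadjusted test treats that spread as noise.

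Weight is a baseline variable that must already be known to compute BMI for eligibility and to set the pump. Using it can sharpen the comparison without new data. At stake is some power and a narrower confidence interval in a trial planned on 54 evaluable patients, and nothing more.

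**Working it through.** **The plan's own figure.** Section 5 allows 10% dropout: 27 / 0.90 = 30 per group, 60 in total, which agrees. The 27 itself cannot be rebuilt, because no difference or SD is given. Solving backwards with the noncentral t (27 per group, two-sided 0.05, 90% power) gives a standardised difference d = 0.899.

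**Background volume (step 9).** The pump is connected after one hour in the recovery unit, so it runs for 23 of the 24 hours.

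- 1, 1.5 and 2 ml/h × 23 h = 23, 34.5 and 46 ml (24, 36 and 48 ml if it starts at the end of surgery).
- At 15 µg / 150 ml = 0.1 µg/ml, this is 2.3, 3.45 and 4.6 µg sufentanil.

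**Assumptions (not in the documents).** Weight is normal with mean 63 kg and SD 9 kg. Patients above 60 and up to 70 kg, for whom step 9 gives no rate, get either 1.5 or 2 ml/h. Demanded volume is independent of background. The stated 90% power refers to total consumption. Two million draws then give:

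- rate 1.5 in the gap: background SD 5.99 ml, R² on weight 0.696, residual SD 3.30 ml;
- rate 2 in the gap: background SD 7.22 ml, R² 0.678, residual SD 4.10 ml.

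**Power after adjustment.** With S the SD of demanded volume:

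- V_total = S² + SD_background²
- V_linear = S² + SD_residual²
- adjusted d = 0.899 × √[V_total / (V_linear × (1 + 1/51))], with 51 degrees of freedom.

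The factor 1 + 1/51 allows for chance imbalance in weight between arms. Example (S = 10, gap rate 1.5): V_total = 100 + 35.9 = 135.9; V_linear = 100 + 10.9 = 110.9; d = 0.899 × √[135.9 / (110.9 × 1.0196)] = 0.986; power 94.4%.

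| S (ml) | V_total | V_linear | Adjusted power | Gain over 90% |
|---|---|---|---|---|
| 10 | 135.9–152.1 | 110.9–116.8 | 94.4–95.6% | 4.4–5.6 |
| 20 | 435.9–452.1 | 410.9–416.8 | 91.1–91.7% | 1.1–1.7 |
| 30 | 935.9–952.1 | 910.9–916.8 | 90.2–90.5% | 0.2–0.5 |
| 40 | 1635.9–1652.1 | 1610.9–1616.8 | 89.9–90.0% | none |

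Simulation with normal demand (4000 trials per cell, standard error about 0.5 point) agrees for S = 10, 20 and 30: linear 94.6–95.6%, 91.4–91.6% and 90.3–90.4%, against 90.1–90.4%, 89.6–90.6% and 90.1–90.3% unadjusted.

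**Offset.** If patients press less when background is higher, cancelling a fraction f of it, both background terms are multiplied by (1 − f)². At f = 0.5, power is 91.1–91.7% for S = 10 and 89.9–90.0% for S = 20. At f = 1 nothing is gained, and the simulated loss with linear weight is 0.2–0.9 point.

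**Bias check.** Under no treatment effect (54 patients; 10/40/50% in the three rate bands; demand SD 10 ml), the mean unadjusted difference was 0.03 ml and the adjusted one 0.02 ml. The standard errors were 3.54 and 2.79 ml, and unadjusted type I error was 5.5%, nominal within simulation error.

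**Skewed demand (simulated).** Adding weight helps each planned test like for like:

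- Lognormal, mean 30, SD 30 ml, 55% reduction: t test 78–80% to linear model 81–82%; Mann-Whitney 80–83% to rank ANCOVA 87–88%.
- Gamma, mean 30, SD 20 ml, 40% reduction: t test 70–72% to 74–75%; Mann-Whitney 63–65% to 70%.

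Replacing the planned test choice by the linear model throughout is not reliably better. Across repeated runs it gave about 80–82% against 79–84% in the lognormal case, and 72–75% against 64–68% in the gamma case.

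**The case against.** The strongest reply is that nothing fails. An unadjusted t or Mann-Whitney test is an ordinary, valid primary analysis, and if the 90% refers to total consumption it meets its target by construction. That stands, and it is why this is an optional improvement.

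The largest gain also rests on the least secure row. At a demand SD of 10 ml, 90% power needs a difference of 0.899 × √135.9 to 0.899 × √152.1, or 10.5 to 11.1 ml. If mean demand were also about 10 ml, the block would have to remove more than all of it. Presses follow need, so some offset is plausible. Rescue oxycodone, if counted, adds variance unrelated to background. Both push towards the small gains.

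Counting the background is an inference: the endpoint is worded as morphine, the pump holds sufentanil and nojan, and no counting rule is given. If patient-demanded dose were intended, the background problem would disappear, but steps 9 and 10 do not record that dose separately.

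A reader might infer that the weight-set infusion biases the comparison, or that the trial is underpowered. Neither follows. Randomisation makes weight independent of arm, and section 5 gives no SD that would show whether this variance was already allowed for.

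**Conclusion.** The point holds as a matter of precision. On the natural reading, the primary endpoint contains a weight-driven component that section 8.2 leaves in the error term. Adjustment is worth roughly 5 power points if demand varies little, 1 to 2 at a demand SD of 20 ml, and essentially nothing from 30 ml upwards. It is worth less with offset, and the downside is under 1 point.

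These sizes rest on assumed weights, an assumed rate in the gap, independent demand, and 90% power referring to total consumption; the documents fix none of them. Severity is minor.

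The missing rate above 60 and up to 70 kg might be read as adding weight to this point. It is a separate dosing clarification and does not affect the case for a covariate.

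**What to change.** In section 8.2, prespecify baseline body weight as a covariate in the primary comparison and keep the planned choice of test:

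- where the t test would be used, fit a linear model of 24-hour consumption on arm plus weight;
- where Mann-Whitney would be used, use a weight-adjusted rank analysis (rank ANCOVA);
- in either case, report the adjusted difference and 95% confidence interval from the linear model.

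List body weight among the data in section 8.1, and state there that total pump dosage is counted, if that is the intention.

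The cost is one degree of freedom and a few lines in sections 8.1 and 8.2. No new measurement is needed.

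Separately, complete step 9 so that every weight, including above 60 and up to 70 kg, has one background rate.
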